#### **6.4. Interim Analysis Plan**

Due to the rare nature of the disease, various investigators have asked whether an interim analysis would be appropriate in this rare population. Since approximately two thirds of the projected subjects have completed the study, we are able to perform an interim analysis using ERR to predict GC responsiveness. Although this is an additional analysis, since the original final analysis plan allowed for an unspecified number of different models, this does not change the overall analysis plan in any substantial way. Nevertheless, trying many models may result in an overfit final result, therefore, for the interim analysis we will try only one flexible model.

We use a linear model to predict the GC responsiveness using either a first, second or third order polynomial of log(ERR) at 4 hours in the model and the final end-prednisone dose of each subject as the GC response as defined in section 3.5.1. The choice between the three models will be made by the one with minimum AIC (Akiake

information criteria). To evaluate the prediction, we will use a leave-one-out cross validated estimate of R squared, where for each fit with a point left out we use the minimum AIC model of the three. Because the entire model finding procedure is cross validated, the estimate of R squared will not be biased upward by using the lowest AIC from the three models. As in the final analysis plan, to test for significance between log(ERR) and GC responsiveness, we test whether the Spearman (i.e., rank) correlation is significantly different from zero, and calculate estimates and associated confidence intervals for Spearman's correlation.

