If the interim model appears to explain the variation of the GC responsiveness (i.e., has a large cross validated R squared), then we can use the interim model to predict the GC responsiveness of the subsequent subjects that enter the study as a validation cohort. Because we expect few additional subjects (<15), our validation would only be able to detect extreme departures from the model. We test for extreme departures from the model by creating a 95% prediction interval and testing whether we can show that significantly less than 95% of the subsequent subjects fall within that prediction interval. For all sample sizes 5 or greater, we have at least 80% power to show that the model fails (the 95% prediction interval covers less than 95% of subsequent responses) if the true proportion that fall within the 95% prediction interval is 50% or less. It is possible that the prediction intervals from the model are so wide that they will not be clinically useful, perhaps as a result of insufficient subjects enrolled, in which case the study will continue since the secondary and exploratory outcomes of the study will continue to be useful for studies of GC effects on eosinophils.

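### Section 6.4 checks the interim model in new subjects only by prediction-interval coverage, which tests calibration and not whether the eosinophil response predicts dose in those subjects

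*Combined protocol and SAP*

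**What the plan says.** Section 6.4 (Interim Analysis Plan) was written when about two thirds of subjects were done: "Since approximately two thirds of the projected subjects have completed the study". It fits a polynomial of order one, two or three in log(ERR) at 4 hours, chosen by AIC, and assesses it by leave-one-out cross-validated R squared. A Spearman correlation with a confidence interval is also planned.

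Later subjects become a validation cohort on one condition: "If the interim model appears to explain the variation of the GC responsiveness (i.e., has a large cross validated R squared". No number is attached to the word large.

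The test in that cohort consists of "creating a 95% prediction interval" and then "testing whether we can show that significantly less than 95% of the subsequent subjects fall within that prediction interval". Its power is stated as follows: "For all sample sizes 5 or greater, we have at least 80% power to show that the model fails", on the condition "if the true proportion that fall within the 95% prediction interval is 50% or less". The section is open about the limit: "Because we expect few additional subjects (<15), our validation would only be able to detect extreme departures from the model". It adds that the intervals may prove too wide to be clinically useful. It names no R squared, correlation or prediction error for the new cohort. It gives no significance level or sidedness for the coverage test.

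**The concern.** The primary objective (section 2.1) is a model showing whether a single-dose challenge can predict GC responsiveness. A validation step should therefore ask whether the predictions track the observed doses in subjects who did not help to build the model.

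Interval coverage asks something else: are the errors about as large as the model says? A model that ignores ERR, predicts the mean dose for everyone and carries an honest interval meets that standard. At a correlation of 0.5 the ERR-based interval is only slightly narrower than that no-predictor interval, since sqrt(1 - 0.25) = 0.87. Most new subjects can fall inside it even if ERR tells nothing about their dose.

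What is at stake is the reading of a non-significant coverage test. Alone, it cannot separate a model that predicts from one that does not, and the plan provides no other result from the new cohort that could.

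**Working it through.** **Inputs.** Section 6.2 expects 30-40 subjects. Two thirds of these is 20-27, which leaves about 10-13 for validation and agrees with the plan's figure of fewer than 15. The only effect size in the protocol is a correlation of 0.5 (sections 6.1 and 6.2), so R squared = 0.25. My assumptions are a normal outcome, a linear true relation, the same marginal distributions in both cohorts, and an exact one-sided binomial test at 0.05.

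**1. The plan's power figure.** Reject at the smallest number of misses r with P(X >= r | n, 0.05) <= 0.05. This gives r = 2 for n = 5-7 and r = 3 for n = 8-15. Power at 50% coverage is P(X >= r | n, 0.5): 81.25% (n=5), 89.1% (n=6), 93.8% (n=7), 85.5% (n=8), 94.5% (n=10), 98.9% (n=13). The minimum over n = 5-199 is 81.25%, so the claim of at least 80% reproduces. At one-sided 0.025 it would not (65.6% at n=6, 77.3% at n=7). At n = 13 the cut-off is 3 misses at either level.

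**2. Coverage when the new cohort shows no association.** Standardise dose to variance 1. The interval half-width is 1.96 x sqrt(1 - R2). If dose is unrelated to ERR in the new cohort, the prediction error has variance 1 + R2. So

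coverage = 2 Phi(1.96 x sqrt((1 - R2)/(1 + R2))) - 1.

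At R2 = 0.25: sqrt(0.75/1.25) = 0.775; 1.96 x 0.775 = 1.518; coverage = 87.1%.

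Coverage of 50% requires 1.96 x sqrt((1 - R2)/(1 + R2)) = 0.6745, so (1 - R2)/(1 + R2) = 0.118 and R2 = 0.882/1.118 = 0.79. The plan's power statement therefore applies to a non-predictive model only if the interim fit was that strong.

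**3. Probability that such a model passes**, P(X < r | n, 1 - coverage):

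| Interim R2 | Coverage | n=5 | n=10 | n=13 | n=14 |
|---|---|---|---|---|---|
| 0 (mean only) | 95.0% | 98% | 99% | 97% | 97% |
| 0.25 | 87.1% | 87% | 87% | 77% | 73% |
| 0.4 | 80.1% | 74% | 68% | 50% | 45% |
| 0.5 | 74.2% | 62% | 50% | 31% | 26% |
| 0.7 | 59.0% | 32% | 15% | 5% | 3% |

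**4. Simulation of the whole procedure** (27 interim subjects, order 1-3 by AIC, t-based interval, leave-one-out R squared, 1,500 runs per setting). Pass rates with no association in the new cohort:

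| True interim R2 | Gate on cross-validated R2 | n=5 | n=10 | n=13 |
|---|---|---|---|---|
| 0.25 | none | 86% | 86% | 76% |
| 0.25 | >= 0.25 | 76% | 72% | 57% |
| 0.5 | none | 65% | 57% | 40% |
| 0.5 | >= 0.25 | 61% | 53% | 35% |
| 0.5 | >= 0.5 | 47% | 40% | 24% |
| 0.7 | none | 37% | 21% | 10% |

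A correct model passes about 94% at n = 13. Further simulations at correlation 0.5 and n = 13 gave 63-67% with a gate of 0.15 and 54-61% with a gate of 0.25.

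**5. A direct measure of prediction.** Use out-of-sample R squared, 1 - sum(y - predicted)^2 / sum(y - interim mean)^2. With 27 interim and 13 new subjects and no gate, it exceeds 0 in 75% of true models at correlation 0.5 and 89% at 0.7. With an interim correlation of 0.5 and no association in the new cohort, it does so in about 20%. It separates the two cases better than coverage does (94% against about 76% passing), though far from perfectly.

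**The case against.** Four points on the other side have force.

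First, a reader might infer that a non-predictive model usually passes whatever the interim fit. The documents do not support that. Validation starts only after a large cross-validated R squared. If large means about 0.5, such a model passes 24% of the time with 13 new subjects and 40% with 10. The claim holds for moderate fits, including the protocol's own correlation, and because large is undefined the plan does not exclude them.

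Second, a reader might infer that the plan never measures prediction. It does: section 6.4 cross-validates the entire model-finding procedure, and sections 6.3 and 6.4 plan Spearman correlations with confidence intervals. The gap is confined to the new cohort. Nor is the model likely to be pure noise: with no association in either cohort, it clears a gate of 0.15 in only 1.6% of simulated trials. The case examined here needs a relation that is real at the interim and absent later at the same centre, which is less common.

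Third, a reader might infer that a pass will be reported as proof of prediction. Section 6.4 does not say so. It frames the test as a way to show failure and states that only extreme departures are detectable. Disclosing low sensitivity does not, however, supply a measure of prediction.

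Fourth, a correct model fails about 6% of the time at n = 13, against 2.45% for exact 95% coverage. That is close to the 5% level assumed here, and the plan states no level, so it is not a separate defect.

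**Conclusion.** The point holds in a limited form. In the validation cohort the plan tests calibration alone. At a correlation of 0.5, with 27 interim and 13 new subjects, a model with no association in the new cohort passes about 76% of the time without a gate and about 55-65% with a gate of 0.15-0.25. At an interim R squared near 0.5 it passes about 25-45%, and at 0.7 or more it mostly fails. The 80% power claim is arithmetically right at one-sided 0.05 but does not cover this failure unless interim R squared is about 0.79.

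These figures rest on normal data, equal marginal distributions, a linear truth and the assumed test level. Prednisone dose is in fact bounded and taken in steps, so real coverage could differ. The matter is a cheap improvement and does not invalidate the plan.

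**What to change.** In section 6.4, add two measures of prediction for the validation cohort:

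- the out-of-sample R squared, 1 - sum(y - predicted)^2 / sum(y - interim mean)^2;
- the Spearman correlation of predicted with observed dose, with its confidence interval.

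Report both as estimates without a pass/fail cut-off. A rule that R squared must exceed 0 would reject about 25% of true models at correlation 0.5, and about a third after a gate of 0.25. Keep interval coverage as a calibration check, and state that failing to reject it does not show that the model predicts. While the section is open, give the level and sidedness of the coverage test and a number for a large cross-validated R squared.

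The cost is a few sentences and a few lines of code, with no new subjects or procedures. The downside is imprecision. By Fisher's z, an observed correlation of 0.5 in 13 subjects gives 0.549 +/- 1.96/sqrt(10), that is -0.07 to 1.17, or roughly -0.07 to 0.82 on the correlation scale. A rank correlation would be somewhat less precise still.

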## **7. Human Subjects Protection**

### **7.1. Study Population**

#### **7.1.1. Rationale for Subject Selection**

New and returning subjects enrolled on Protocol #94-I-0079 who have documented HES, AEC >1500/ $\mu$ L on  $\leq$  10 mg prednisone equivalent daily and are candidates for GC therapy will be recruited for this protocol. Subjects receiving higher prednisone doses at baseline will be excluded to maximize the likelihood that the steroid challenge will have observable effects. Subjects with chronic eosinophilic leukemia, including those with PDGFR-associated disease, will also be excluded since imatinib is first line therapy for this condition.

#### **7.1.2. Recruitment Plan**

Individuals contacting the investigators for evaluation of HES as well as subjects already enrolled in Protocol #94-I-0079 (Eosinophil Activation and Function in Parasitic Infections and other Conditions with Increased Tissue or Blood Eosinophilia in Humans) will be considered for participation in this protocol.

## **7.2. Justification for Eligibility of Special Populations**

### **7.2.1. Exclusion of Pregnant Women**

Subjects who are pregnant, including those for whom GC are clinically indicated, will be excluded from participation in this study because of the increased risk of gestational diabetes in the setting of prolonged GC exposure in pregnancy. These subjects will be referred to their referring/treating physician for management.

### **7.2.2. Exclusion of Children Weighing <48 kg**

Children younger than 18 years of age weighing <48 kg will be excluded from the study due to limitations of maximal blood draw over time for research purposes.

### **7.2.3. Inclusion of Children Weighing ≥48 kg**

Children younger than 18 years of age weighing ≥48 kg will be eligible to enroll in this study because HES is a genetic disease that can affect children. Therefore, there is important information about this disease and the use of GCs as treatment to be learned from pediatric participants. Additionally, children stand to benefit from this study the same as adults.

## **7.3. Potential Risks**

### **Venipuncture**

The drawing of blood may be associated with discomfort, occasional bruising at the site of puncture, and rarely, fainting. All blood will be drawn from arm veins.

### **IV line insertion**

The risks of having an IV inserted including pain, bruising, swelling, and in rare instances, fainting, thrombosis, or infection.

### **Prednisone**

Prednisone (or its equivalent) is commonly used to treat a wide variety of disorders, including HES. The common side effects of prednisone are well-described and include increased appetite, insomnia, fluid retention, indigestion, headache, facial swelling, menstrual irregularities, and visual changes. When used over extended periods of time, GCs (such as prednisone) may cause weight gain, cataracts, myopathy, osteoporosis, glucose intolerance, increased risk of infections such as *P. jiroveci*, and can affect mood. Abrupt cessation of prednisone may cause headaches, vomiting, hypotension, fatigue, and in severe cases, may result in loss of consciousness and even death. If participants become severely ill or need to undergo surgery during the prednisone taper, their doses may need to be increased temporarily. There is evidence that participants who take high doses of prednisolone may secrete the steroid in breast milk. Waiting to breastfeed for 3-4 hours after receipt of prednisolone reduces this risk. In any

case, there are no known effects of corticosteroids in breastfed infants. Participants on long-term dosing will be monitored closely for these side effects. In addition, for subjects that will be on greater than 30-mg prednisone for 3 weeks or longer (ie those on the increased 60-mg dose), standard *P. jiroveci* prophylaxis will be instituted. Similarly, evidence-based approaches for GC bone loss prevention or treatment will be followed according to the latest ACR 2010 recommendations for prevention of GC induced osteoporosis(19, 20).

#### **7.4. Potential Benefits**

Since the study is designed to evaluate the degree of response to GC's in the treatment of hypereosinophilic syndrome, subjects may or may not benefit from therapy. The information learned from this study may improve understanding of how GCs can be used to treat HES, which may lead to improvements in clinical care of these patients.

#### **7.5. Informed Consent Process**

Informed consent is a process where information is presented to enable persons to voluntarily decide whether or not to participate as a research subject. It is an on-going conversation between the human research subject and the researchers that begins before consent is given and continues until the end of the subject's involvement in the research. Discussions about the research will provide essential information about the study and include: purpose, duration, experimental procedures, alternatives, risks and benefits. Subjects will be given the opportunity to ask questions and have them answered.

Subjects will sign the informed consent document prior to undergoing any research procedures. The subjects may withdraw consent at any time throughout the course of the trial. A copy of the informed consent document will be given to the subjects for their records. The researcher will document the signing of the consent form in the subject's medical record. The informed consent process will emphasize that the quality of subjects medical care will not be adversely affected if they decline to participate in this study.

##### **7.5.1. Assent of Children**

Where deemed appropriate by the clinician and the child's parent(s) or guardian, the child will also be included in all discussions about the trial and age-appropriate language will be used to describe the procedures and tests involved in this study, along with the risks, discomforts and benefits of participation. Verbal assent will be obtained as appropriate for children ages 8 years and older. Children under the age of 18, but who are age 8 or older will be asked to sign an age appropriate assent form. Children under the age of 8 will not be required to provide assent as they typically do not have the ability to fully understand the nature of research. The consent/assent process will be documented in the child's medical record, including the assessment of the child's ability to provide assent (verbal versus written) as applicable. All children will be contacted

after they have reached the age of 18 to determine whether they wish to continue on the trial and informed consent will be obtained from them at that time.

### **7.5.2. Consent for minors when they reach the age of majority**

When a pediatric subject reaches age 18, continued participation (including ongoing interactions with the subject or continued analysis of identifiable data) will require consenting of the now adult with the standard protocol consent document to ensure legally effective informed consent has been obtained.

If re-consent is not feasible, we request waiver of informed consent to continue to use data and/or specimens for those individuals who become lost to follow up or who have been taken off study prior to reaching the age of majority.

Requirements for Waiver of Consent consistent with pre-2018 45 CFR 46.116 (d):

- (1) The research involves no more than minimal risk to the subjects.
  - a. Analysis of samples and data from this study involves no additional risks to subjects.
- (2) The research could not practicably be carried out without the waiver or alteration.
  - a. Considering the length of time between the minor's last contact with the research team and their age of majority, it will likely be very difficult to locate them again. A significant reduction in the number of samples analyzed is likely to impact the quality of the research.
- (3) The waiver or alteration will not adversely affect the rights and welfare of the subjects.
  - a. Retention of these samples or data does not affect the welfare of subjects.
- (4) Whenever appropriate, the subjects will be provided with additional pertinent information after participation.
  - a. We only request a waiver of consent for those subjects who have been lost to follow-up or who have been taken off study prior to reaching the age of majority.

### **7.5.3. Telephone Consent Process**

Subjects with HES will be screened for this study on Protocol 94-I-0079. If for any reason a subject chooses not to or is unable to sign the Informed Consent during a scheduled visit on Protocol 94-I-0079 but he/she chooses to enroll on this protocol, permission to consent subjects over the telephone may be permitted. In these instances, permission to email, mail or fax the consent document will be obtained from the subject. Once consent is received, the subject is instructed to call the investigator for discussion of the study and consent document. The study will be thoroughly explained with ample time for questions or concerns related to participation. Informed consent will be obtained by the principal investigator or a designated associate

investigator on this protocol. The subject will identify him/herself by name and date of birth, and state that he/she gives consent to participate in this study. The staff member will verify the subject's name and the verbal consent to participate. Upon completion of the telephone call, the manner of obtaining consent and the names of the person administering and providing consent will be documented in the medical record, signed and dated. The subject must sign and date the consent in his/her possession. This signed and dated consent must be sent to the investigator. No testing will occur without this consent. Once received, the consent will be checked for accuracy and signed by the NIH investigator/designee. The signed consent will then be filed in the medical record.

## **7.6. Subject Confidentiality**

All records will be maintained in a locked file in the Clinical Center and/or in the Medical Records Department of the NIH where they are accessible only to authorized personnel.

All records will be kept confidential to the extent provided by federal, state, and local law. The study monitors and other authorized individuals may inspect all documents and records required to be maintained by the investigator, including but not limited to, medical records. Records will be kept locked and data will be coded. Any personally identifiable information maintained for this study will be kept on restricted-access computers and networks. Personally identifiable information will only be shared with individuals authorized to receive it under this protocol. Individuals not authorized to receive personally identifiable information will be provided with coded information only, as needed. Clinical information will not be released without written permission of the participant, except as necessary for monitoring by the IRB, NIAID, and OHRP.

## **8. Adverse Event Reporting Plan**

### **8.1. Specification of Safety Parameters**

HES is a complex multisystem disorder. Exacerbations of symptoms or signs related to eosinophilia are expected to occur during this protocol and will be recorded, but not reported as AEs. Similarly, side effects of GC are well-described (see section 7.3) and are expected to occur during this protocol. Although GC administration at the doses to be used in this study is considered standard of care for HES, we will record but not report disease-related AEs, and record and report all research-related AEs (including expected events from the GCs) per NIH Human Research Protections Program (HRPP) Policy 801 described in section 8.3.

### **8.2. Reporting Procedures**

Unanticipated problems, non-compliance, and other reportable events will be reported to the IRB according to HRPP Policy 801.

The principal investigator will report UPs, major protocol deviations, and deaths to the NIAID clinical director according to institutional timelines.

